7.2 Safety outcomes

(1) The ejection fraction evaluated by ultrasonic cardiogram within 72 hours.

[figure not shown]
(2) Death rate within 90 days.

(3) Intracranial hemorrhage and symptomatic intracranial hemorrhage within 7 days.

(4) Blood pressure fluctuation within 24 hours.

(5) Infarction edema volume evaluated by cranial CT at 24 hours.

8. Study flow diagram

AIS: acute ischemic stroke; IVT: intravenous thrombolysis; NS: normal saline.

9. Study periods

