Safety Outcomes	
 1. Ejection fraction within 72 hours. 2. Mortality within 90 days 3. Proportion of intracranial hemorrhage (ICH) and symptomatic ICH within 7 days. 4. Infarction volume at 24 hours after randomization. 5. Blood pressure fluctuation within 24 hours.
Trial Design	NS-STAR is a prospective, multicentre, randomised, open-label, blinded outcome reading, Phase II trial (PROBE design). Subjects included are randomly assigned into the NS group and the control group. Follow-up is performed at baseline, 24 hours, 7 days, 30 days and 90 days after randomization. The outcome assessors are blinded to the allocation

	assignment.
Trial Population	Patients with acute ischemic stroke treated by intravenous thrombolysis
Sample Size	240
Inclusion Criteria	
 1. Acute ischemic stroke. 2. Age 18-80 years. 3. Pre-stroke mRS≤1. 4. NIHSS score 0-25 5. Onset-to-needle time≤4.5 h. 6. Sign the informed consent.
Exclusion Criteria	
 1. Thrombolysis contraindication. 2. Allergy to alteplase. 3. intention to undergo emergency endovascular treatment. 4. Any terminal illness such that patients would not be expected to survive>1 year. 5. Poor compliance. 6. Participating in other clinical trials within previous 3 months.
Withdrawal Criteria	
 1. Acute heart failure during interventions. 2. Hypertensive crisis during interventions. 3. Edema, such as pulmonary edema, limb edema and water intoxication. 4. Other severe complications that should terminate the interventions immediately. 5. Stroke mimics. 6. Decide to undergo emergency endovascular treatment during interventions. 7. Refuse subsequent treatment and follow-up.
Trial Cycle	All included patients are followed-up at baseline, 24 hours, 7 days, 30 days and 90 days after randomization, respectively.
Treatment Regimens	Eligible patients are randomly (a ratio of 1:1) assigned into the NS group: undergoing immediate 2000 mL intravenous infusion of NS after intravenous thrombolysis at a speed of 200 mL/h, or the control group: receiving

	200-400ml of NS after intravenous thrombolysis. A standard therapy according to Chinese guidelines for diagnosis and treatment of acute ischemic stroke 2023 will be performed during the whole treatment period.

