Procedure	
Before intravenous thrombolysis: The investigators will collect demographic characteristics, medical history, blood pressure, brain imaging (either computer tomography or magnetic resonance imaging), neurological measurements (NIHSS score and mRS score), haematological examination (blood routine, creatinine, urea, brain natriuretic peptide, etc.), laboratory examination (S100-β, brain derived neurotrophic factor and myeloperoxidase) and other pertinent information.
 
After intravenous thrombolysis: The informed consent will be obtained and patients will be randomly assigned into the NS group and the control group. The investigators will then collect blood pressure and neurological measurements (NIHSS score).
 
24-48 hours after randomization: Brain imaging (either computer tomography or magnetic resonance imaging) will be performed at 24 hours. The 24-hour NIHSS score will be assessed and cerebrovascular events occurring within 24 hours will be recorded. Blood routine and laboratory examination (S100-β, brain derived neurotrophic factor and myeloperoxidase) will also be collected.
 
72 hours after randomization: Cerebrovascular imaging (either computer tomography angiography or magnetic resonance angiography) and an ultrasonic cardiogram will be conducted within this period.
 
7 days after randomization: Neurological measurements (NIHSS score and mRS score) will be evaluated. Cerebrovascular events during this 7-day period will also be recorded.
 
30 days after randomization: The mRS score and Barthel index score will be assessed and cerebrovascular events or other adverse events will be recorded via a telephone interview.

	90 days after randomization: The mRS score and Barthel index score will be again assessed and cerebrovascular events or other adverse events will be recorded via a telephone interview.
Concomitant Treatment	Guideline based treatment.

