3.4 Randomization and masking

All patients are enrolled consecutively and randomized in 1:1 ratio to receive NS 2000ml or 200-400ml using a computer-generated randomization code. Sealed envelopes containing the allocation information (NS or control) will be labeled with sequential numbers prepared by an investigator who does not know screening of subjects. The researchers will enroll potential patients with a sequential number of opaque sealed envelopes, which will be opened only after obtaining informed consent. It is ensured that investigators are masked to the treatment allocation.

This is an open label trial, so we adopt a partial blinding strategy where the clinical assessors are blinded but the operators are not. That is, the neurological functional scores, imaging tests and laboratory assessments are assessed by investigators blinded to the intervention and grouping. The operators responsible for NS infusion to the patients are unblinded.

4. Trial Flow Chart

STUDY PROTOCOL									
	Enrollment	IVT ending	Interventions	Follow-up					
TIMEPOINTS	-1 h	0 h	0-10 h	24 h	48 h	Day 3	Day 7	Day 30	Day 90
ENROLLMENT									
Eligible Screen	X								
Informed Consent		X							
Allocation			X						
Termination Screen				X					
INTERVENTIONS									
NS 2000 mL				→					
NS 200-400 mL				→					
ASSESSMENT									
Baseline Data	X								
NIHSS score	X	X		X		X			
Cranial CT	X				X				
Blood Indices	X				—				
Laboratory examination	X				—				
Ultrasonic Cardiogram					—				
Cranial MRA/CTA					—				
Blood pressure					—				
mRS						X	X	X	

IVT: intravenous thrombolysis; NS: 0.9% normal saline; NIHSS: Institute of Health Stroke Scale; CT: computed tomography; MRA: magnetic resonance angiography; CTA: computed tomography angiography; mRS: modified Ranking scales.

5. Interventions

All patients within 4.5 hours from the definite onset time will be screened by the criteria of IVT recommended by European Stroke Organisation (ESO) guidelines.[20]

During thrombolysis, the patient or his certigiers will decide whether to participate in this trial. If they agree, an informed consent for NS-STAR trial will be signed, and allocation will proceed.

Participants will be allocated into two arms:

the NS group, undergoing immediate 2000 mL intravenous infusion of NS after IVT at a speed of 200 mL/h.

the control group, receiving 200-400ml of NS after IVT.

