6.2 Imaging tests

Cranial CT scans are performed before IVT and 24 hours after randomization. The infarction area is confirmed using CT maps and the infarction volume is calculated by 3D-Slicer (Version 4.6.2, <https://www.slicer.org/>). Magnetic resonance angiography (MRA), CT angiography (CTA), or carotid artery ultrasound are used to evaluate cranial vessels.

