9.2 Treatment periods

After IVT administration, patients are randomized into two groups: receiving intravenous NS 2000ml and NS 200-400ml respectively. Therapy follows the Chinese guidelines for diagnosis and treatment of acute ischemic stroke 2023[21]. Blood pressures are recorded at 0 hour, 10 hours, 12 hours and 24 hours after randomization. NIHSS scores are assessed immediately after IVT administration and 24 hours after randomization. Cranial CT scan is performed at 24 hours. Haematological examinations including blood routine and laboratory biomarkers (S100- β , MBP and GFAP), and routine urine test are conducted at 24-48 hours after randomization.

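### Any intracranial hemorrhage is compared over 7 days, but the only scheduled post-treatment brain scan is at 24 hours, so silent bleeding after that is not ascertained uniformly

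*Combined protocol and SAP*

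**What the plan says.** The outcome appears in three places with the same window: section 7.2 item 3 ("Intracranial hemorrhage and symptomatic intracranial hemorrhage within 7 days"), section 2.3, and the synopsis under Safety Outcomes ("Proportion of intracranial hemorrhage (ICH) and symptomatic ICH within 7 days"). Section 7.2 names a method for ejection fraction and for edema volume, but none for hemorrhage.

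Post-treatment brain imaging is described consistently as one scan at 24 hours:
- Section 6.2: "Cranial CT scans are performed before IVT and 24 hours after randomization".
- Section 9.2: "Cranial CT scan is performed at 24 hours".
- Synopsis, Procedure: "Brain imaging (either computer tomography or magnetic resonance imaging) will be performed at 24 hours".
- Section 3.1 also has one CT at 24 hours, counted from thrombolysis rather than randomization. This makes no difference here.

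The other imaging is of vessels. In the synopsis, under the 72-hour entry: "Cerebrovascular imaging (either computer tomography angiography or magnetic resonance angiography) and an ultrasonic cardiogram will be conducted within this period". Section 6.2 widens the choice: "Magnetic resonance angiography (MRA), CT angiography (CTA), or carotid artery ultrasound are used to evaluate cranial vessels". At day 7, section 9.3 and the synopsis list NIHSS and mRS only.

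On masking, section 3.4 says: "This is an open label trial, so we adopt a partial blinding strategy where the clinical assessors are blinded but the operators are not". It adds that imaging is assessed by blinded investigators. Section 11.2 analyses safety outcomes on the full analysis set and estimates a relative risk for dichotomous endpoints.

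**The concern.** Any hemorrhage includes bleeding without symptoms, which exists in the data only if someone images the brain. Up to the 24-hour scan every patient is looked at in the same way. After it, a silent hemorrhage counts only if that patient is scanned again, and the plan sets no trigger for such scans and does not ask for them to be counted. The 7-day proportion therefore joins a uniform measure to a selective one, and section 11.2 would compare the mixture between arms as if ascertainment were the same throughout.

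Two things can go wrong. If one arm is re-scanned more often, its count rises with no true difference. If both arms are re-scanned equally but seldom, a real late excess is diluted. Unequal re-scanning is plausible: section 10.1 lists severe cerebral edema among the adverse events considered associated with the interventions, which could lead clinicians to image one arm more readily. The trial sets out to show that the infusion is safe (section 2.1), so the hemorrhage comparison should be interpretable.

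**Working it through.** **The plan's own figures.** The documents give no expected hemorrhage rate and no rate of unscheduled scanning, so there is no figure to reproduce. The only design number used below is 120 patients per group (section 11.1).

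**Coverage by scheduled imaging**

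| Period | Scheduled imaging | Read for hemorrhage? |
|---|---|---|
| Randomization to 24 h | Brain scan at 24 h (3.1, 6.2, 9.2, synopsis) | Yes: 3.1 makes antiplatelet use depend on it |
| 24 to 72 h | Vessel imaging at some point up to 72 h; CTA, MRA or, in 6.2, carotid ultrasound | Not stated |
| 72 h to day 7 | None | Not applicable |

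By the clock, 24 of 168 hours (14%) end in a scheduled brain scan and 144 hours (86%) follow it. That is a share of time, not of risk.

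**Illustration on assumed rates.** Let E be the proportion with hemorrhage found by the 24-hour scan, L the proportion with a first, silent hemorrhage between 24 hours and day 7, and s the proportion re-scanned. Assume re-scanning is unrelated to silent bleeding and detects it when present. Then the observed proportion is E + L × s, and the true proportion is E + L.

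*A. No true difference, unequal re-scanning.* Assume E of 5–10%, L of 2–8%, and s of 15% in control and 45% in NS. The difference is L × (0.45 − 0.15).
- L = 2%: 2 × 0.30 = 0.6 points. With E = 10%: control 10 + 2 × 0.15 = 10.3%, NS 10 + 2 × 0.45 = 10.9%, RR 10.9/10.3 = 1.06.
- L = 8%: 8 × 0.30 = 2.4 points. With E = 5%: control 5 + 8 × 0.15 = 6.2%, NS 5 + 8 × 0.45 = 8.6%, RR 8.6/6.2 = 1.39.
- Scan rates reversed: RR 10.3/10.9 = 0.94 and 6.2/8.6 = 0.72.

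Per 120 patients these differences are 120 × 0.006 = 0.7 and 120 × 0.024 = 2.9 patients. The 95% half-width for the larger case is 1.96 × √[(0.062 × 0.938 + 0.086 × 0.914)/120] = 6.6 points. For 10.3% v 10.9% it is 7.8 points.

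*B. True late excess, equal re-scanning.* Assume E = 8% in both arms and L = 8% in NS v 3% in control. The true RR is 16/11 = 1.45.
- s = 10%: 8.8/8.3 = 1.06
- s = 20%: 9.6/8.6 = 1.12
- s = 30%: 10.4/8.9 = 1.17
- 24-hour scan only: 8/8 = 1.00

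The last line matters for the remedy: the 24-hour comparison is uniform, but it cannot see a late excess at all.

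**The case against.** The strongest case on the other side is that little is at stake. The 24-hour scan comes after thrombolysis and after the whole infusion (2000 mL at 200 mL/h takes 10 hours), and nothing in the documents suggests that hemorrhage risk is spread evenly over 7 days. Patients stay in hospital for at least 7 days, and symptomatic bleeding would usually prompt a scan. Hemorrhage is one of five unranked safety outcomes, which section 2.3 calls secondary, and section 11.2 treats secondary analyses as exploratory. Even with a threefold gap in scanning, the assumed bias is about 1 to 3 patients per 120, well inside the confidence interval. All of this stands. It limits the importance of the point but does not make the 7-day comparison uniform.

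A reader might infer more than the documents support:
- *That arm-aware staff order the later scans.* No section says who orders them. Section 3.4 names only those giving the infusion as unblinded. In an open-label trial the ordering clinicians probably know the arm, but that is an inference.
- *That nothing could show bleeding between 24 hours and day 7.* A CTA or MRA done after 24 hours may show blood. Its timing and type vary, so it narrows the gap unevenly rather than closing it.
- *That 86% of the risk is unobserved.* The figure is clock time only.
- *That the bias runs against saline.* The direction is unknown.
- *That the 24-hour count should replace the 7-day count.* Case B shows that this would reduce a true RR of 1.45 to 1.00 in the compared measure.

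**Conclusion.** The point holds in a limited form. Any hemorrhage is defined over 7 days, but uniform ascertainment ends at the 24-hour brain scan, and the gap is firmest from 72 hours onward. Blinded reading protects how a scan is interpreted, not who receives one. The weakness concerns mainly silent hemorrhage; symptomatic hemorrhage is much less affected.

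The documents do not allow the size or direction of any bias to be determined. The 0.6 to 2.4 points in case A and the dilution from 1.45 to 1.06–1.17 in case B rest wholly on assumed hemorrhage and scanning rates and show only what is possible. Case B needs no unequal behaviour by staff, so the point does not depend on showing that scan ordering is influenced by the arm. It leaves the primary outcome untouched and is worth correcting chiefly because the correction is cheap.

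**What to change.** In section 7.2 item 3, section 2.3, the synopsis and section 11.2:

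- (a) Add any intracranial hemorrhage on the scheduled 24-hour scan or on any earlier post-randomization scan, read blind, as the prespecified, uniformly ascertained between-arm comparison.
- (b) Keep symptomatic intracranial hemorrhage within 7 days. The documents give no definition of it, which is a separate gap.
- (c) Still report any intracranial hemorrhage within 7 days by arm, labelled as clinically detected after 24 hours, together with the number of patients per arm who had an unscheduled brain scan, so that a late excess is not hidden.

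The cost is wording in four places, one CRF item for unscheduled brain scans and one extra analysis line. No additional scan is needed. The downside is that comparison (a) says nothing about silent bleeding after 24 hours, and it is uniform only to the extent that the 24-hour scan is actually done in every patient.

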9.1 Screening periods

Before IVT administration, enrollment screening and collection of demographic features, medical history, onset-to-needle time, cranial CT imaging, blood pressure, neurological measurements (NIHSS score and mRS score), haematological examinations (blood routine, creatine, urea, BNP, electrolyte, coagulation function and laboratory biomarkers including S100- β , BDNF and MPO), and other information are necessary.

9.2 Treatment periods

After IVT administration, patients are randomized into two groups: receiving intravenous NS 2000ml and NS 200-400ml respectively. Therapy follows the Chinese guidelines for diagnosis and treatment of acute ischemic stroke 2023[21]. Blood pressures are recorded at 0 hour, 10 hours, 12 hours and 24 hours after randomization. NIHSS scores are assessed immediately after IVT administration and 24 hours after randomization. Cranial CT scan is performed at 24 hours. Haematological examinations including blood routine and laboratory biomarkers (S100- β , MBP and GFAP), and routine urine test are conducted at 24-48 hours after randomization.

9.3 In-hospital periods

Ultrasonic cardiogram is performed at 72 hours after randomization. NIHSS score and mRS score are assessed at 7 days after randomization.

9.4 Follow-up periods

Neurological measurements including mRS score and Barthel index are assessed via a telephone interview at 30 and 90 days. Cerebrovascular events and death events are recorded carefully at this time. All the adverse events should be recorded and tracked until properly resolved.

10. Adverse events monitoring

10.1 Adverse events (AEs)

All AEs information should be carefully recorded and tracked until properly resolved. AEs in this trial include acute heart failure, hypertensive crisis, edema (such as severe cerebral edema, pulmonary edema, limb edema and water intoxication) and other severe complications during and after interventions that are considered to be associated with the interventions.

10.2 Serious adverse events (SAEs)

SAEs are any untoward medical occurrence (whether related to interventions or not) meeting any of the following criteria: (1) fatal (AEs causes death); (2) life-threatening; (3) causing or prolonging hospitalization; (4) disability or organ function impairment.

10.3 Safety assessment

For AEs and SAEs occurring in this study, the following factors will be evaluated for safety: (1) severity criteria for AEs; (2) causal relationship between the event and intervention; (3) anticipation of events.

10.4 Severity categorization and relationship definitions of AEs

10.4.1 Severity categorization

(1) Grade I, mild

A transient symptoms or the event that requires only minimal therapeutic interventions. The event does not affect usual activities of daily living.

(2) Grade II, moderate

A significant symptoms or the event that requires additional specific therapeutic interventions. The event affect usual activities of daily living, causing discomfort or disability but with no profound or permanent risk of harm to the participant.

(3) Grade III, severe

A profoundly severe symptoms or the event that requires intensive therapeutic interventions. The event profoundly affects or interrupts usual activities of daily living, causing disability and even posing permanent risk of harm to the participant.

(4) Grade IV, life-threatening

The event leads to death at any time.

(5) Grade V, death

Death.

10.4.2 Causal relationship between the event and the intervention

(1) Definitely related

AEs occur during the intervention and/or the AEs disappear when the intervention discontinues. The occurrence of AEs cannot be explained by factors other than the intervention. Similar AEs re-occur when re-use of the intervention.

(2) Probably related

AEs occur during the intervention and/or the AEs relieve or not when the intervention discontinues.

The occurrence of AEs can or cannot be explained by factors other than the intervention. It is not sure similar AEs re-occur when re-use of the intervention.

(3) Probably unrelated

AEs do not occur during the intervention and/or the AEs do not relieve when the intervention discontinues. The occurrence of AEs can or cannot be explained by factors other than the intervention.

It is not sure similar AEs re-occur when re-use of the intervention.

(4) Definitely unrelated

AEs do not occur during the intervention and/or the AEs do not relieve when the intervention discontinues. The occurrence of AEs can be explained by factors other than the intervention. Similar AEs do not re-occur when re-use of the intervention.

(5) Unjudged

The judgment cannot be made due to incomplete information.

11. Statistics

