3.2.3 Withdrawal criteria

- (1) Acute heart failure during interventions.
- (2) Hypertensive crisis during interventions.
- (3) Edema, such as severe cerebral edema, pulmonary edema, limb edema and water intoxication.
- (4) Other severe complications that should terminate the interventions immediately.
- (5) Stroke mimics.
- (6) Decide to undergo emergency endovascular treatment during interventions.
- (7) Refuse subsequent treatment and follow-up.

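### Section 10.4.2: both *Definitely* causality grades depend on re-using an infusion that is given once, and the two *Probably* grades do not separate events reliably

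*Combined protocol and SAP*

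**What the plan says.** Section 10.3 lists three factors to be evaluated for every AE and SAE. One is the "causal relationship between the event and intervention". Section 10.4.2 supplies the scale: four grades plus *Unjudged* for incomplete information. Each of the four grades is a short run of sentences on timing and relief, other explanations, and re-use.

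- *Definitely related*: onset during the intervention and/or disappearance when it stops; no other explanation; and "Similar AEs re-occur when re-use of the intervention".
- *Probably related*: "AEs occur during the intervention and/or the AEs relieve or not when the intervention discontinues"; another explanation may or may not exist; recurrence on re-use is uncertain.
- *Probably unrelated*: "AEs do not occur during the intervention and/or the AEs do not relieve when the intervention discontinues"; another explanation may or may not exist; recurrence on re-use is uncertain.
- *Definitely unrelated*: the same timing and relief sentence as *Probably unrelated*; another explanation exists; no recurrence on re-use.

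Section 5 describes one course per arm: "the NS group, undergoing immediate 2000 mL intravenous infusion of NS after IVT at a speed of 200 mL/h", and "the control group, receiving 200-400ml of NS after IVT". No section describes a repeat course or a rechallenge. The withdrawal criteria in section 3.2.3 include "Other severe complications that should terminate the interventions immediately", with no restart step.

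**The concern.** A causality scale should place each assessable event in one grade, by criteria that can be observed in the trial. Here two of the four substantive grades rest on an observation the trial does not plan to make. The other two rest on wording that either overlaps or leaves gaps, depending on how and/or is read.

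Section 2.1 says the study intends to demonstrate safety. Section 10.1 names acute heart failure, hypertensive crisis and edema as AEs. Of these, heart failure and pulmonary or limb edema are not listed as events among the section 7.2 safety outcomes, so their reporting runs mainly through the AE section. Section 10.1 also admits other severe complications as AEs only if they are judged to be associated with the intervention. How relatedness is judged can therefore affect which of those events are counted, as well as how they are labelled.

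**Working it through.** The plan gives no figure to reproduce here. The check applies the definitions to every possible type of event.

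**Inputs.**
- Exposure (section 5): 2000 mL ÷ 200 mL/h = 10 h, matching the 0-10 h intervention column of the flow chart; 200-400 mL in controls. One course in each arm.
- Event features used by section 10.4.2: onset during the infusion (yes/no), relief on stopping (yes/no), other explanation (yes/no). This gives 2 × 2 × 2 = 8 profiles.
- Re-use result: unknown for everyone, since no re-use is planned.
- The sentences within a grade are taken as all required. And/or is read first as inclusive or, then as strict and.

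**Step 1, the *Definitely* grades.** One needs recurrence on re-use and the other needs its absence. Neither is observed, so each grade takes 0 of 8 profiles under both readings. The re-use sentence cannot be treated as met by default, because the scale has its own wording for an uncertain re-use result and places it only in the two *Probably* grades.

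**Step 2, the *Probably* grades.** Both accept events with or without another explanation, so that feature never changes the grade. The 8 profiles reduce to four rows of two.

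| Onset during infusion | Relief on stopping | Profiles | And/or read as or | And/or read as and |
|---|---|---|---|---|
| yes | yes | 2 | related only | related |
| yes | no | 2 | related and unrelated | related |
| no | yes | 2 | related and unrelated | no grade |
| no | no | 2 | related and unrelated | unrelated |

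Totals, read as or: *Probably related* 2+2+2+2 = 8 of 8; *Probably unrelated* 2+2+2 = 6 of 8. All 6 meet both grades, and no profile is unrelated only.

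Totals, read as and: *Probably related* 2+2 = 4 of 8; *Probably unrelated* 2 of 8; no grade 2 of 8; no overlap. Onset during the infusion becomes a condition of both related grades, so an event that starts later can never be graded related. Section 10.1 counts complications both during and after the intervention.

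**Step 3, would deleting only the re-use sentences be enough?** With and/or read as or, *Definitely related* then takes 3 of 8 profiles and *Definitely unrelated* 3 of 8. *Probably related* still takes 8 of 8, and 7 of 8 profiles fall in two or more grades. The remaining wording has to change as well.

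**The case against.** A reader might infer that a report of no *Definitely related* events is guaranteed. The text does not go that far. Section 10.4.2 never states that all sentences of a grade are mandatory. Re-exposure is unplanned but not expressly barred: a paused infusion could be resumed, or saline given later. The withdrawal criteria cover listed or severe complications and do not cover every AE. This objection stands against the word guaranteed. It does not rescue the scale. If re-exposure did occur and and/or is read as or, a known recurrence would give a grade to only 3 of 8 profiles, and so would a known non-recurrence; the other 5 would have none in either case.

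A reader might also infer that every event is *Probably related*, or that the scale cannot sort at all. The first holds only if and/or means or. The second fails because onset during the infusion with relief on stopping gets one grade under either reading, and *Unjudged* covers incomplete information. The no-grade row under the and reading is also partly artificial, since relief on stopping has little meaning for an event that begins after the infusion has ended. Setting those 2 profiles aside closes the gap (2 − 2 = 0), but such an event still cannot be graded related.

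Finally, a reader might infer that the trial's safety conclusion is biased. The documents do not support this. The section 7.2 outcomes (ejection fraction, death, intracranial hemorrhage, blood pressure, edema volume) do not use the grade. Section 10.2 defines SAEs whether related or not, and section 11.2 plans no analysis by relatedness. *Definitely unrelated* is just as unreachable, so no harm can be dismissed through it, and the or reading is permissive towards attribution. The protocol does not say who assigns the grade, so a claim that unblinded staff would steer it is speculation.

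**Conclusion.** Wrong as written. If all sentences of a grade are required and nobody is re-exposed, both *Definitely* grades are empty (0 of 8 profiles each), whichever way and/or is read. This follows from the re-use sentences alone. The *Probably* grades are unreliable in a way that depends on the reading: with or, 8 of 8 profiles are related and 6 of those 8 also unrelated; with and, there is no overlap, but 2 of 8 have no grade and later-onset events are shut out of the related grades.

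The consequence is confined to attribution of AEs and SAEs under section 10.3 and to which other severe complications count as AEs under section 10.1. The between-arm safety comparisons in section 7.2 are unaffected.

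**What to change.** In section 10.4.2, delete the re-use sentences from all grades. Replace the and/or construction, and the clauses that accept both relief and no relief or both presence and absence of another explanation, with mutually exclusive and exhaustive criteria. Base these on whether timing is plausible, explicitly including onset after the infusion, and whether another cause is more likely. For example:

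- Related: a reasonable possibility that the infusion contributed, meaning that neither ground for unrelated applies.
- Unrelated: no reasonable possibility, because the timing is implausible or another cause is more likely.
- Unjudged: information incomplete.

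Three levels are an example; a finer scale is acceptable if its levels exclude one another. Grading from records with the arm removed is optional, since a timing judgement needs infusion details that may reveal the arm.

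The cost is rewording the protocol and CRF, and re-grading from existing records any events already graded. No dose, endpoint or sample size changes.
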